The statistical analyses and reporting will adhere to the CONSORT guidelines. All tests will be two-sided, a p-value <0.05 will be considered significant, and all confidence intervals will have 95% coverage. All analyses will be conducted on a modified intention-to-treat basis only including participants receiving at least the first dose of the study medication. In a double-blind trial, this approach is unbiased while increasing precision. Analyses will not be adjusted for covariates unless there are significant differences in baseline characteristics between study arms.

Baseline Characteristics

A description of the baseline characteristics will be presented by treatment arm. Categorical variables will be summarized by frequencies and percentages. Percentages will be calculated according to the number of patients for whom data are available. Continuous variables will be summarized using mean+/-standard deviation or median (interquartile range) based on the distribution of the data.

Analysis of Primary Outcome

We will compare repeated measures of lactate levels at each time point (0h, 6h, 12h, 24h) between arms using a linear mixed-effects model with an independent variance-covariance matrix to account for the correlation of within-patient repeated measures. Covariates in the model include treatment arm, time (as a categorical variable with four levels, defined as baseline, 6 hours, 12 hours, and 24 hours), and the interaction between treatment arm and time. Linear contrasts will be used to estimate the mean difference between treatment arms for each time point. If a patient dies before 24 hours, levels will be imputed by carrying forward the last known value before the event with a 20% penalty. A sensitivity analysis will be performed in which patients who die before 24 hours are assigned the last known value before the event without a penalty.

Analysis of Secondary Outcomes

Lactate levels over 72 hours

To test for a difference in absolute lactate level values, we will compare means or medians, as appropriate, between arms using either a Student's t-test or a Wilcoxon rank-sum test, respectively, at 6, 12, 24 and 72 hours.

Change in oxygen consumption (VO₂) over 48 hours

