To investigate the association between treatment and gas metabolism data (VO₂, VCO₂ and RQ) in the first 48 hours after ROSC, we will compare the area under the curve (AUC) for each oxygen consumption variable between the treatment arms. The AUCs for the oxygen consumption variables are influenced by the number of minutes of data available, which varies between patients. To account for this, AUCs for each patient will be adjusted by dividing by the number of minutes of oxygen consumption data available for that patient. Additionally, the AUCs for the VO₂ and VCO₂ variables are influenced by the weight of the patient, and thus will also be adjusted by dividing by the bodyweight of the patient, in kilograms. The median AUCs will be compared between treatment groups using the univariate Wilcoxon rank-sum test. To

control for the known effect of temperature on oxygen consumption, we will use quantile regression to compare median AUCs between patients using the treatment assignment as the predictor and average temperature as a covariate. To examine the association between treatment and the VO₂:Lactate Ratio, we will use a linear quantile mixed model (LQMM) with the VO₂:Lactate Ratio as the outcome variable, treatment as the predictor variable and temperature as the covariate. To account for clustering of VO₂:Lactate Ratio and temperature measurements within patients, we will add a random intercept for each patient to the LQMM. We will not control for vasopressor use or sedation in the above analyses unless use of these agents is significantly imbalanced between arms.

Pyruvate dehydrogenase (PDH), S100, NSE, SOFA score, creatinine, and cellular oxygen consumption rate levels over 72 hours

To test change over time, we will compare repeated measures of each outcome listed above at each time point (0h, 24h, 72h) between arms using a linear mixed-effects model with an independent variance–covariance matrix to account for the correlation of within-patient repeated measures. Covariates in the model include treatment arm, time, and the interaction between treatment arm and time. Linear contrasts will be used to estimate the mean difference between treatment arms for each time point. To test for a difference in absolute values between arms, we will compare means or medians, as appropriate, using either a Student’s t-test or a Wilcoxon rank-sum test, respectively, at 24 and 72 hours.

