Mortality, Cerebral Performance Category (CPC) Score, and Cerebral Performance Category-Extended (CPC-E) Score at hospital discharge, 30 days, and 90 days

Proportions of patients who do not survive to hospital discharge, 30 days, and 90 days will be compared between treatment arms using Fisher’s exact test. Fisher’s exact test will also be used to compare the proportion of patients who have a favorable CPC score at the same time points, with favorable CPC score defined as a score of 1-2 and unfavorable a CPC of 3-5. CPC-E will be analyzed between treatment arms as a continuous variable in survivors to the time point of interest using either a Student’s t-test or a Wilcoxon rank-sum test, based on the distribution of the data.

Acute renal failure in the first 7 days after study drug initiation

Acute renal failure in the first 7 days after study drug initiation will be determined using the Kidney Disease Improving Global Outcomes (KDIGO) criteria for Stage 3 acute kidney injury/kidney failure. These criteria are as follows:

1. An increase in creatinine to $\geq 3 \times$ baseline (baseline defined as enrollment [post-arrest pre-study drug] creatinine value) OR
2. An increase in creatinine by $\geq 0.3\text{mg/dL}$ from baseline to $\geq 4\text{mg/dL}$ OR
3. Initiation of renal replacement therapy

Patients who die before 7 days and who do not meet the above criteria before death or transition to comfort measures only status will be classified as not having acute renal failure. Proportions of patients who have renal failure will be compared between groups using Fisher's exact test. Patients who already have end-stage renal disease (defined as being on dialysis/renal replacement therapy prior to arrest) will be excluded from the acute renal failure analysis.

Additional Planned Analyses

Pre-planned subanalyses of the primary outcome and of the secondary outcomes of mortality and VO_2 will be performed stratified by arrest duration, dichotomized into <15 minutes and ≥ 15 minutes and in the group of patients with baseline thiamine deficiency (plasma vitamin B1 level ≤ 7 nmol/L). Based on feedback from the DSMB, we will also perform subanalyses based on 0 hour lactate, stratified by ≤ 5 and >5 .

Analysis of Adverse Events

Rates of serious expected and unexpected adverse events will be reported by arm assignment. Proportions of patients with adverse events will be compared between the treatment arms using Fisher's exact test.

Statistical Software

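### CPC-E is compared in survivors only, and the fixed-time secondary tests of lactate, SOFA and biomarkers have no rule for deaths

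*SAP*

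**What the plan says.** The SAP treats death differently from one outcome to the next.

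- **Primary lactate, to 24 h** (*Analysis of Primary Outcome*): "If a patient dies before 24 hours, levels will be imputed by carrying forward the last known value before the event with a 20% penalty". In a sensitivity analysis, "patients who die before 24 hours are assigned the last known value before the event without a penalty".
- **Secondary lactate** (*Lactate levels over 72 hours*): t-test or "Wilcoxon rank-sum test, respectively, at 6, 12, 24 and 72 hours". No death rule, and no word on whether the primary imputation applies.
- **PDH, S100, NSE, SOFA, creatinine and cellular oxygen consumption** (section of that name): for the longitudinal analysis, "we will compare repeated measures of each outcome listed above at each time point (0h, 24h, 72h) between arms using a linear mixed-effects model"; for absolute values, t-test or "Wilcoxon rank-sum test, respectively, at 24 and 72 hours". Neither analysis has a death rule.
- **CPC-E** (section on mortality, CPC and CPC-E): analysed "as a continuous variable in survivors to the time point of interest".
- **CPC and mortality** (same section): Fisher's exact test, with "favorable CPC score defined as a score of 1-2 and unfavorable a CPC of 3-5" and no survivor restriction stated.
- **Acute renal failure**: patients who die without meeting the criteria count as not having the event.

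**The concern.** A t-test or rank-sum test needs a value for each patient. Where death removes the value and no rule replaces it, the test runs on patients alive and sampled. Randomisation balances the arms at entry; it does not balance the survivors if treatment changes who survives. An arm that keeps more of its sickest patients alive carries their high lactate, high SOFA and poor CPC-E into the comparison, while the other arm loses such patients to death. The arm with more deaths can then look better.

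The SAP itself expects early deaths, since it sets rules for them for primary lactate and for renal failure. The gap therefore falls within the SAP's own scope. It also leaves it unclear whether the 24 h lactate in the secondary table and in the primary model will rest on the same set of patients.

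**Working it through.** The SAP states no figure on this point, so there is none to reproduce. The check is a comparison of the rules, followed by two illustrations of direction and size.

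**1. Which rule covers which time point**

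| Comparison | Deaths before 24 h | Deaths from 24 to 72 h |
|---|---|---|
| Primary lactate, 0–24 h | last value + 20% | not applicable |
| Secondary lactate, 6, 12, 24 h | not stated | not applicable |
| Secondary lactate, 72 h | not stated | not stated |
| SOFA and biomarkers, 24 h | not stated | not applicable |
| SOFA and biomarkers, 72 h | not stated | not stated |

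CPC-E at discharge, 30 and 90 days excludes the dead by explicit rule.

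**2. Does the mixed model for SOFA and the biomarkers settle it?** It too has no death rule. The SAP names an independent covariance structure. If that means independent errors within patient, and time is categorical (stated for the primary model, not for this one), a model with arm, time and their interaction returns the observed mean per arm and time. The 72 h contrast is then again among patients with a 72 h value. If a random intercept is meant, earlier values of patients who later die contribute, but their values after death are treated as ordinary missing data. Neither reading corrects the separate fixed-time tests.

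**3. Direction, by a SOFA example.** All inputs are assumed: 72 h mortality 30% control and 20% thiamine; the extra 10% of survivors on thiamine score 12; all other survivors score 7.

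- Survivor means: control 7.0; thiamine (0.70×7 + 0.10×12)/0.80 = 6.1/0.80 = 7.625. Thiamine looks 0.6 worse.
- Survivors-only rank comparison: 0.10/0.80 = 12.5% of thiamine survivors exceed every control survivor and the rest tie. P(thiamine worse) + ½P(tie) = 0.125 + 0.5×0.875 = 0.5625. Above 0.5 means thiamine looks worse.
- Death ranked worst: thiamine worse in 0.20×0.70 + 0.10×0.70 = 0.21 of pairs; control worse in 0.30×0.80 = 0.24; tied in 0.20×0.30 + 0.70×0.70 = 0.55. P(thiamine worse) + ½P(tie) = 0.21 + 0.275 = 0.485. The sign reverses.
- With death given a score d, the arm means are 0.3d + 4.9 (control) and 0.2d + 6.1 (thiamine), so thiamine is better for any d above 12.

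**4. Size, by a lactate simulation.** From the SAP: 46 per arm (92/2), and 24 h lactate with mean 2.9 and SD 2. Assumed: log-normal shape, no treatment effect on lactate, the mortality pairs below, and a correlation of 0.3 or 0.6 between log lactate and the severity that drives death. There were 4,000 runs. Differences are treated minus control in mmol/L; each range covers both correlations. The penalised column multiplies a decedent's simulated lactate by 1.2, as a stand-in for last value plus 20%.

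| Mortality, control vs treated | Survivors-only difference | Wilcoxon rejection | Difference, decedents × 1.2 |
|---|---|---|---|
| 20% vs 10% | +0.09 to +0.17 | 5.2–6.6% | about −0.07 |
| 30% vs 20% | +0.07 to +0.15 | 5.5–6.8% | −0.07 to −0.08 |
| 30% vs 15% | +0.13 to +0.23 | 5.4–9.4% | −0.08 to −0.11 |
| 40% vs 25% | +0.11 to +0.20 | 5.8–8.5% | −0.09 to −0.10 |
| 40% vs 20% | +0.16 to +0.28 | 6.4–11.3% | −0.13 to −0.14 |

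The simulation error of a rejection rate near 5% is √(0.05×0.95/4000) = 0.3 percentage points, so the lowest rates do not differ from the nominal 5%. For scale, the lactate difference planned at 24 h is 2.9 − 1.94 = 0.96. The survivors-only shift is about 0.07/0.96 = 7% to 0.28/0.96 = 29% of that, and in the opposite direction.

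**The case against.** - **The text is silent rather than wrong.** A reader might infer that all these comparisons are planned in survivors only. The SAP says so for CPC-E alone. For lactate, SOFA and the biomarkers it is the default when nothing else is specified. This stands.
- **Two death rules for 24 h lactate.** A reader might infer that the same measurement is analysed under two conflicting rules. The SAP gives one rule with a labelled sensitivity variant, and the secondary test has none. If the imputed values carry over, the data are identical. What can be said is that carry-over is undefined.
- **Not every SOFA or biomarker analysis is survivors-only.** The mixed model can use values obtained before death. This is true under a random-intercept reading, but it does not repair the fixed-time tests.
- **Mortality and CPC sit beside CPC-E.** Any survival difference would be visible, and CPC-E is openly a description of survivors. This has weight, but the SAP still plans a between-arm test of CPC-E with no caution on its interpretation.
- **The figures are constructed.** In the SOFA example the medians are 7 in both arms, and the simulation supposes survival differences of 10 to 20 percentage points. The rank test nevertheless responds to the upper tail (0.5625). The shift in lactate is modest against an SD of 2, and rejection rates are only mildly inflated in most scenarios.
- **The 20% penalty is not neutral.** With no true lactate effect it favours the better-surviving arm by about 0.07 to 0.14. This stands, and it is a reason not to stretch the rule beyond 24 h.

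**Conclusion.** The point holds as a gap in secondary analyses. CPC-E is compared in a group selected after randomisation. The fixed-time tests of secondary lactate, SOFA and biomarkers fall into the same position by default, because no death rule is given. If treatment affects survival, the better-surviving arm can look worse, and for 24 h lactate the sign can depend on whether decedents are dropped or imputed with the penalty.

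The direction rests on sicker patients being both likelier to die and higher on the measure. The size rests on assumed mortality and correlation, since the SAP gives neither. Over the range tried it is 0.07 to 0.28 mmol/L, with Wilcoxon rejection between 5.2% and 11.3%. If treatment does not affect mortality, this mechanism does not arise. The primary analysis has its own rule and sensitivity analysis and is not touched. This is a cheap improvement, not a threat to the main result.

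**What to change.** 1. **Secondary lactate at 6, 12 and 24 h:** apply the primary death rule, with its no-penalty sensitivity analysis, so that primary and secondary results rest on the same values.
2. **Lactate at 72 h, SOFA and CPC-E:** add a Wilcoxon test in which patients who died before the time point share the worst rank. Report it beside the survivor-only comparison, and label the latter descriptive. Patients alive but not measured stay missing and are not ranked as deaths.
3. **Biomarkers:** report by arm, at each time, the number alive and the number sampled.
4. **Do not carry the last-value-plus-20% rule to 72 h.** It was written for deaths before 24 h; a patient who died at 60 h would receive the 24 h value plus 20%.

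The cost is a few sentences in the SAP and trivial code. The downside is that a worst-rank result mixes death with severity and partly overlaps the mortality and CPC analyses, so the survivor-only summary is still needed for description.

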The analysis method for the primary endpoint will be linear mixed-effects modeling (LMM). This type of modeling is used in longitudinal or repeated-measures studies to take into account the correlation of within-subject measurements and can optimize the power. In this case, each subject will have lactate measurements at multiple time points, which are correlated. Since LMM will be used for the analysis, we have also used LMM for power analysis for this endpoint. We evaluated approximately 61 post-arrest patients in our databases for which we had lactate measurements over 24 hours and that matched the inclusion/exclusion criteria for the current proposal. We observed that the post-CA patients have a mean lactate of 3.8 ± 2.2 mmol/L at 6 hours, 3.5 ± 2.2 at 12-hours, and 2.9 ± 2 at 24-hours. We took a conservative position to assume that the potential effect size (the mean difference of lactate between the two groups) will be 33%. That is, we assumed that the mean lactate level at the three different time points were 2.55, 2.35, and 1.94. We then simulated the longitudinal data with the assumption that the variance-covariance structure of the lactate data followed a compound-symmetry structure with between-subject variance of 2.07. The linear-mixed effects model was used on the simulated data to obtain the estimated F statistic, numerator, and denominator degrees of freedom. From these estimates, the non-centrality parameter was computed and used to obtain the power. To obtain 80% power, with type-I error of 0.05, 66 subjects (33 thiamine, 33 placebo) will be needed to detect the stated difference over 6, 12, and 24-hours. We

secondarily performed calculations using the difference in means approach at the time point of 6 hours where we anticipate maximal effect of thiamine. At this time point, a reduction by 33% yields a power of 80% with a total sample size of 92. To be conservative we will use the larger sample size of 92 patients to ensure adequate power. With this sample size, the linear-mixed model will have 92% power to detect differences between groups with the same assumptions.

Statistical Analysis

General Principles

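### Subgroup effects are to be examined stratum by stratum with no treatment-by-subgroup interaction, so no planned analysis estimates whether the effect differs between subgroups

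*SAP*

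**What the plan says.** Under Additional Planned Analyses the SAP lists three subgroup factors.

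- **Arrest duration:** the primary outcome, mortality and VO2 are to be analysed "stratified by arrest duration, dichotomized into <15 minutes" and the complementary stratum of 15 minutes or more.
- **Thiamine status:** the same outcomes are to be analysed "in the group of patients with baseline thiamine deficiency", defined by a plasma level. No comparison with non-deficient patients is named.
- **0 h lactate:** following DSMB feedback, "we will also perform subanalyses based on 0 hour lactate, stratified by ≤ 5 and >5".

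That section gives no treatment-by-subgroup term, no rule for comparing strata, no subgroup sizes and no statement that the analyses are exploratory. General Principles sets one rule for the whole document: "All tests will be two-sided, a p-value <0.05 will be considered significant". The only interaction anywhere in the SAP is in the mixed models, for the primary outcome and for the biomarker and organ-function outcomes: treatment arm, time "and the interaction between treatment arm and time".

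**The concern.** A subgroup factor is examined to learn whether the treatment effect depends on it. That question concerns the difference between two effects, and separate analyses within strata neither estimate that difference nor test it. A result that is significant in one stratum and not in the other is weak evidence of a difference, because each stratum has only part of the sample and the two tests will often disagree by chance.

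At stake is a claim that thiamine works only in, say, short arrests or high-lactate patients, resting on a chance pattern of p-values. For thiamine deficiency the gap is of another kind: only one group is analysed, so nothing in the plan could show that its effect differs from that in other patients.

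**Working it through.** **Inputs.** From Sample Size Calculations: "mean lactate of 3.8 ± 2.2 mmol/L at 6 hours"; a 33% reduction, so 0.33 × 3.8 = 1.254 mmol/L (1.25 from the printed means); 92 patients, 46 per arm; stated power 80% for the 6 h means and 92% for the mixed model. From General Principles: two-sided 0.05. The split between strata is my assumption, since the SAP gives none.

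**Reproducing the plan's own power.**
- 6 h means: non-centrality = 1.254 / (2.2 × √(2/46)) = 2.73; power = Φ(2.73 − 1.96) = 78%, against 80% stated. An unrounded SD of about 2.15 closes the gap.
- Mixed model: scaling the stated 80% at 66 patients to 92 gives 2.802 × √(92/66) = 3.31; power = Φ(3.31 − 1.96) = 91%, against 92% stated. A direct compound-symmetry calculation from the printed SDs gives about 87 to 88%.

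**Probability that exactly one stratum is significant.** Give both strata the same absolute effect. A stratum holding share f of the patients has non-centrality = (1.96 + z for the overall power) × √f. If p1 and p2 are the two stratum powers, P(exactly one significant) = p1(1 − p2) + p2(1 − p1).

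| Split | 6 h (80% overall): stratum powers | Exactly one | Mixed model (92% overall): stratum powers | Exactly one |
|---|---|---|---|---|
| 50/50 | 51%, 51% | 50% | 66%, 66% | 45% |
| 60/40 | 58%, 43% | 51% | 74%, 57% | 47% |
| 70/30 | 65%, 34% | 55% | 80%, 45% | 53% |

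A t-test calculation from the printed mean and SD agrees. With 23 per arm in each stratum, power is 47% and 2 × 0.47 × 0.53 = 50%. With 32 and 14 per arm it is 54%.

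**Smaller effects.** At half the planned effect, with 23 per arm per stratum, the t-test power at 6 h is 15.6%, and 2 × 0.156 × 0.844 = 26% (28% when scaled from the stated 80%; about 34% when scaled from the stated 92%). With no effect, 2 × 0.05 × 0.95 = 9.5%.

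**The alternative.** When the absolute effect is the same in both strata, an interaction test at 0.05 is positive in 5% of trials. Simulation gave 4.8 to 5.2% at every split tried. Its power is limited: with even strata, SE = 2.2 × √(2/23) × √2 = 0.917. A 1.25 mmol/L difference between strata is then 1.36 standard errors, giving about 27% power.

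**Scale for the 0 h lactate factor.** The planned effect is relative. If 6 h control means in the two lactate strata differ by 2 mmol/L (an assumption), a uniform 33% reduction gives absolute effects that differ by 0.66 mmol/L. That is 0.66 / 0.917 = 0.72 standard errors, and a raw-scale interaction test then rejects in about 11% of trials. The figure is about 6% if the means are 1 mmol/L apart and about 19% if they are 3 apart.

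**The case against.** The SAP never says that strata will be contrasted by their p-values. That reading combines the word for stratification with the general significance rule. The SAP also promises 95% confidence intervals and linear contrasts, so a careful author could report stratum estimates without claiming a difference. This is fair, and the point is put as an inference. But no other subgroup method is stated, the analyses are not exempted from the p<0.05 rule, and confidence intervals within strata still do not estimate the difference between them.

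A reader might infer that any uniform effect will look different between strata about half the time, in all the subgroup analyses. The SAP does not support that. The figure depends on the full planned effect being present and on a reader treating one significant stratum as a difference. It concerns lactate only, because no effect is assumed for mortality or VO2, and it cannot arise in the deficiency analysis, where only one group is named.

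It can also be said that an interaction test with about 27% power settles little. That stands, and it is a reason to report the interaction estimate with its interval and to label the analyses exploratory. It does not make separate tests a valid substitute.

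Finally, a raw-scale interaction term could itself mislead for 0 h lactate, as the working shows. That stands too and is built into the remedy.

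**Conclusion.** The point holds in limited form. The SAP plans analyses within strata, and in one case within a single group, without any analysis that measures whether the effect differs. The 45 to 55% range rests on four assumptions: the full planned lactate effect; the same absolute size in both strata; splits between 50/50 and 70/30; and each stratum judged at p<0.05. It falls with a smaller effect but stays above 5% even with none. The primary analysis is untouched. The weakness lies in what could be claimed from the subgroups, and it should be corrected before analysis.

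**What to change.** For each subgroup factor, fit one model to the full analysis sample:

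- **Lactate:** add arm × time × subgroup, with its lower-order terms, to the mixed model.
- **Mortality:** use a logistic model with arm × subgroup.
- **VO2:** add arm × subgroup to the planned quantile regression.
- **Thiamine status:** compare deficient with non-deficient patients in the same way, if numbers allow. The exclusion of known or highly suspected deficiency may leave the deficient group small.
- **0 h lactate:** test the interaction on the log (ratio) scale, or report both scales.

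Report each interaction estimate with its 95% confidence interval and p-value. Show stratum estimates with intervals but without significance claims. Label all these analyses exploratory and state that interaction power is low.

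The cost is SAP wording and a few model terms, with no new data. The SAP says that it was submitted before any data analysis began, so the change belongs at that stage. The downside is that a non-significant interaction will not show that the effect is uniform.
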